If nonintubation anaesthesia for laryngomicrosurgery can be performed with nerve block and intravenous anesthetic medicine, the cardiovascular risks may decrease because of avoiding CO2 retention by maintaining patient's spontaneous breathing function. The feasibility and safety of nonintubated LMS with spontaneous breathing was evaluated in this case series.

Method

We divide the patients who need laryngoscopy microsurgery into three groups. The first group is general anesthesia with endotracheal tube intubation, the second group is non-intubation with muscle relaxant administered; the third group is non-intubation without muscle relaxant.

The three groups will perform arterial blood oxygen analysis (collecting PaO₂, PaCO₂, pH, HCO₃-data) before intubation, before muscle relaxant administration and before SLNB, after the operation and 15 minutes after transferring to the recovery room, as well as the pressure of the surgeons and the degree of completion of the operation to analyze the difference between intubated general anesthesia and non-intubation anesthesia.

Results

Last year, we passed the in-hospital plan (2021/04/07) and have been included (Table 1). There are 15 males and 14 females, all of whom have completed the trial phase without complications. Group 1 earns 11 people, Group 2 earns 7 people, and Group 3 earns 11 people.

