Ho3: There is less sore throat in the nonintubation group than in the intubation group.

Ho4: Non-intubation and no muscle relaxation may lead to less postoperative pulmonary complications.

Ho5: In the non-intubation group, no muscle relaxants are more suitable for long-term surgery than those with muscle relaxants.

Statistical analysis (the statistical analysis tool will use IBM SPSS version 20):

- 1 、 The sample characteristic data will be expressed as average, SD, and median, and the category variables will be displayed in the form of count and percentage.
- 2 、 The 95% confidence interval will show the original data and the change from the baseline.
- 3 、 The difference between the three groups was analyzed using one-way ANOVA to analyze the comparison between the intubation and non-intubation groups for drug administration, the presence or absence of complications, the severity and

the degree of completion of the operation.

- 4 ‧ The differences between the groups will be evaluated by chi-square test or Fisher's exact test.
- 5 ‧ Unless otherwise stated, all statistical tests will be two-way and evaluated at a significance level of 0.05.

Sample size calculation :

The main purpose of the study will focus on the completion of surgery and the occurrence of complications. In order to obtain the total number of participants in the study, a sample size will be calculated to detect a difference in incidence reduction of 25%. A statistical power of 80%, a 5% alpha and up to 10% possible sample loss. Therefore, each group will require 30 patients (90 in total). Considering the number of patients undergoing laryngoscope microsurgery each year, we estimate that there may be a total of 45 patients within a year. After meeting the inclusion criteria and obtaining patient consent, 45 patients will be included in the treatment plan in the first year, and the remaining sample size will be completed next year.

Primary outcome(2nd year) :

- 1 ‧ Less carbon dioxide retention and less hypercapnia.
- 2 ‧ Reduce postoperative lung complications.

Statistics from 10/20/2020 to 5/11/2021 :

Table I-i. Baseline demographics

Variable	G1(n=11)		G2(n=7)		G3(n=11)		p-value
	Mean	SD	Mean	SD	Mean	SD	
Age	52.0	13.9	46.9	8.4	51.7	14.2	0.66
BMI	26.4	5.5	24.5	3.5	25.1	2.5	0.78

Table I-ii. Baseline demographics

Variable	G1(n=11)		G2(n=7)		G3(n=11)		p-value
	n	(%)	n	(%)	n	(%)	
Sex							
male	7.0	63.6	3.0	42.9	5.0	45.5	0.60
female	4.0	36.4	4.0	57.1	6.0	54.5	
ASA							

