ASA I	3.0	27.3	3.0	42.9	9.0	81.8	0.04
ASA II	8.0	72.7	4.0	57.1	1.0	9.1	
ASA III	0.0	0.0	0.0	0.0	1.0	9.1	
Medical history							
HTN	3.0	27.3	0.0	0.0	4.0	36.4	0.20
CVA	1.0	9.1	0.0	0.0	0.0	0.0	0.43
CVD	1.0	9.1	0.0	0.0	3.0	27.3	0.22
DM	1.0	9.1	0.0	0.0	2.0	18.2	0.46
Endocrine	1.0	9.1	2.0	28.6	1.0	9.1	0.43
Genitourinary	0.0	0.0	1.0	14.3	0.0	0.0	0.20
HPL	1.0	9.1	1.0	14.3	0.0	0.0	0.47
Neurologic	0.0	0.0	1.0	14.3	1.0	9.1	0.47
Hepatitis B	1.0	9.1	1.0	14.3	0.0	0.0	0.47

Table I-ii. During the acceptance period, group 3 included 1 ASA3 case, and the remaining groups have not yet encountered ASA3 cases.

Table II. Arterial blood oxygen changes during surgery

Variable	G1(n=11)		G2(n=7)		G3(n=11)		p-value
	Mean	SD	Mean	SD	Mean	SD	
Before surgery							
pH_1	7.4	0.0	7.3	0.0	7.4	0.0	0.34
PaCO2_1	49.5	2.5	53.6	9.5	51.3	6.5	0.58
PaO2_1	321.2	79.6	451.9	108.6	377.5	196.6	0.14
SO2_1	99.7	0.8	99.9	0.0	99.8	0.4	0.50
HCO3-_1	28.3	1.7	28.6	3.3	28.8	1.6	0.67
In surgery							
pH_2	7.3	0.0	7.2	0.1	7.3	0.0	0.00
PaCO2_2	54.4	7.6	86.4	21.7	55.5	10.8	0.00
PaO2_2	186.9	64.0	321.8	128.2	341.9	136.9	0.02
SO2_2	99.3	1.1	99.6	0.5	99.7	0.5	0.48
HCO3-_2	27.7	1.9	31.8	4.1	29.1	2.7	0.06
After surgery							
pH_3	7.4	0.0	7.4	0.1	7.4	0.0	0.07
PaCO2_3	43.6	4.0	45.1	9.0	43.3	5.7	0.78
PaO2_3	123.3	63.1	110.8	16.1	116.3	29.6	0.77
SO2_3	98.0	1.5	98.2	1.0	98.3	1.4	0.81
HCO3-_3	25.8	1.7	26.3	2.9	27.0	2.5	0.55

Table II. During the operation, the PaCO2 value of the second group was >80mmHg.

Table III. Discomfort after surgery

Variable	G1(n=11)		G2(n=7)		G3(n=11)		p-value
	n	(%)	n	(%)	n	(%)	
Sore throat	3.0	27.3	0.0	0.0	4.0	36.4	0.20
Hoarseness	6.0	54.5	6.0	85.7	7.0	63.6	0.39
Difficulty breathing	0.0	0.0	0.0	0.0	1.0	9.1	0.43

Table III. One case in group 3 reported dyspnea in the recovery room. In most cases of laryngoscope surgery, the voice is required to be silenced after the operation, so the case cannot make a sound.

Table IV. Side effects after surgery

Variable	G1(n=11)		G2(n=7)		G3(n=11)		p-value
	n	(%)	n	(%)	n	(%)	
nausea	0.0	0.0	0.0	0.0	1.0	9.1	0.43
Vomiting	1.0	9.1	0.0	0.0	1.0	9.1	0.71
Nausea and vomiting	0.0	0.0	0.0	0.0	1.0	9.1	0.43

Table IV. One patient in group 1 had the side effect of vomiting.

In group 3, 1 case had nausea and vomiting.

Table V. Three stages of vital signs

Variable	G1(n=11)		G2(n=7)		G3(n=11)		p-value
	Mean	SD	Mean	SD	Mean	SD	
Before surgery							
BT	36.0	0.5	36.3	0.4	36.2	0.5	0.61
SpO2	98.8	1.3	98.1	1.5	97.7	2.1	0.46
NBPs	136.5	11.2	121.7	7.5	124.0	18.5	0.04

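### Item 4 leaves chi-square or Fisher's exact test open, and the 29-patient tables use uncorrected Pearson chi-square even in single-event rows; for outcomes still rare at 90 patients the choice can decide significance (minor)

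*Protocol*

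**What the plan says.** The Protocol, section C, Statistical analysis, item 4, reads "The differences between the groups will be evaluated by chi-square test or Fisher's exact test". It does not say when each test applies. Item 5 adds that "all statistical tests will be two-way and evaluated at a significance level of 0.05". Item 3 assigns one-way ANOVA to a list that includes whether complications occurred and how completely the operation was done, so items 3 and 4 overlap on those outcomes.

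The sample size paragraph makes completion of surgery and occurrence of complications the main purpose, and plans that "each group will require 30 patients (90 in total").

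The same section prints results for the first 29 patients: "Group 1 earns 11 people, Group 2 earns 7 people, and Group 3 earns 11 people". Tables I-ii, III, IV, VI and VII carry 24 categorical p-values without naming the test. Two examples are "Difficulty breathing 0.0 0.0 0.0 0.0 1.0 9.1 0.43" (Table III) and "ASA I 3.0 27.3 3.0 42.9 9.0 81.8 0.04" (Table I-ii). Surgery completion was complete in all 29 and is printed as N/A.

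**The concern.** Offering both tests is ordinary protocol wording, and a selection rule may sit in a statistical analysis plan that is not shown. The open choice alone would not be a point. What the Protocol does show is how the choice was filled: the printed p-values do not use the exact test even where one event is spread over groups of 11, 7 and 11.

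If the same practice continues to 90 patients, comparisons of the rarer complications and of surgical failures would rest on an approximation that is poor at such counts. Two analysts following item 4 could then report different conclusions from the same data.

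**Working it through.** **Inputs.** Counts from Tables I-ii, III, IV, VI and VII; group sizes 11, 7 and 11; planned 30 per group; two-sided 0.05.

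**1. Reproducing a printed value.** Difficulty breathing is 0/11, 0/7, 1/11. Expected events are 11/29 = 0.379, 7/29 = 0.241 and 0.379. For a binary outcome, Pearson chi-square = [sum of (O − E)²/E over the event cells] / (1 − event fraction).
- Sum: 0.379 + 0.241 + (1 − 0.379)²/0.379 = 1.636.
- Divide by 28/29: 1.695.
- With 2 degrees of freedom, p = exp(−1.695/2) = 0.4285, printed as 0.43.

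The exact test (Fisher-Freeman-Halton) adds the probabilities of all tables no more likely than the observed one. With one event these are 11/29, 7/29 and 11/29. The observed table is among the most likely, so p = 1.00.

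**2. All rows.** All 24 printed values (11 in Table I-ii, 3 in III, 3 in IV, 6 in VI, 1 in VII) match uncorrected Pearson to two decimals, and none matches the exact test. Every table has at least a third of its cells with expected count below 5.

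| Row | Counts | Pearson | Exact |
|---|---|---|---|
| Difficulty breathing | 0/0/1 | 0.43 | 1.00 |
| Poor vision | 1/0/1 | 0.71 | 1.00 |
| CVD history | 1/0/3 | 0.22 | 0.41 |
| Sore throat | 3/0/4 | 0.20 | 0.22 |
| ASA class | 3 × 3 table | 0.037 | 0.015 |
| Procedure type | 5 × 3 table | 0.14 | 0.08 |
| Lesion site | 6 × 3 table | 0.16 | 0.10 |

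The shift has no constant direction. ASA is below 0.05 under both tests and the other 23 rows are above it under both.

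**3. Which outcomes stay sparse at 30 per group.** Assuming the current pooled rates persist, expected events per group are:
- difficulty breathing: 30 × 1/29 = 1.0
- poor vision: 30 × 2/29 = 2.1
- sore throat: 30 × 7/29 = 7.2, so not sparse

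Incomplete surgery has occurred in none of 29, so any failures would be rare.

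**4. Can the tests disagree at 30 per group?**
- 0/0/3: Pearson = 6/(1 − 3/90) = 6.207, p = exp(−3.103) = 0.045. Exact p = 3 × C(30,3)/C(90,3) = 12,180/117,480 = 0.104.
- 0/5/5: Pearson = 5/(1 − 10/90) = 5.625, p = 0.060. Exact p = 0.042.
- 1/2/7: 0.031 against 0.070.
- 0/0/4: 0.015 against 0.032, so both reject.

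Ignoring group order, 50 binary patterns fall on opposite sides of 0.05.

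**5. Type I error over all outcomes, equal true rates, 30 per group (full enumeration).**

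| Event rate | Pearson | Exact |
|---|---|---|
| 3% | 3.1% | 0.8% |
| 5% | 3.6% | 1.8% |
| 10% | 4.0% | 3.6% |
| 24% | 4.9% | 4.2% |

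Over rates of 1% to 50%, Pearson ranges from 0.6% to 5.2%. With equal rates of 3% to 10% the tests disagree in about 0.7% to 2.3% of trials. Under assumed true rates of 0%, 0% and 9.1% (the current difficulty-breathing figures, resting on one event) they disagree in about 23%, and power is 52% for Pearson and 29% for the exact test.

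**The case against.** The case against is substantial, and most of it stands. A reader might infer four stronger things that the Protocol does not support.

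- **That conclusions are already wrong.** They are not. No printed decision at 0.05 changes. The findings drawn under Table VIII concern blood gases, which are continuous. Eleven of the 24 rows are baseline characteristics and only six are postoperative complaints.
- **That Pearson inflates false positives at 90 patients.** The 10.4% chance of 0/0/3 or its equivalents applies only given exactly three events in total. Over all outcomes the error rate is about 5% or below.
- **That the plan was breached or the more favourable p-value was picked.** Item 4 permits Pearson, and it was used throughout, even where the exact test gives the smaller value (ASA, procedure type, lesion site).
- **That every complication will be too sparse.** Sore throat will not be, at about 7 expected events per group.

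It can also be said that the exact test is no free improvement, since it loses power where events are rarest. That is true and belongs in the decision. What survives is that the document prints asymptotic p-values at expected counts of 0.24 while offering an exact alternative, and leaves open a choice that can decide a result on a rare outcome.

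**Conclusion.** The point holds as a minor one. The printed categorical p-values are poor approximations, some by a wide margin (0.43 against 1.00), without affecting any current decision. At 90 patients the choice of test can decide significance for difficulty breathing, poor vision or incomplete surgery. How often depends on the true rates: about 1% to 2% of trials if the groups are alike at 3% to 10%, and about 23% under the assumed 0%, 0%, 9.1% pattern. These figures assume 30 analysed patients per group and comparison of all three groups in one test. The projections of sparseness rest on 29 patients and are rough.

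**What to change.** - **Item 4:** state that categorical comparisons with any expected count below 5 use the Fisher-Freeman-Halton exact test and all others use Pearson chi-square without correction.
- **Item 3:** remove presence of complications and degree of completion from the one-way ANOVA, so that this rule governs them. Changing item 4 alone would leave the two items in conflict over these outcomes.
- **Tables:** name the test under each table and reissue the 29-patient categorical p-values. First reconcile the sore throat counts: the Results summary reports one patient in groups 1 and 3, while Table III shows 3 and 4.

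The cost is a few sentences and a rerun. The real downside is that the exact test is conservative with very rare events (type I error of 0.8% at a 3% event rate, and the power loss shown above), so a non-significant result on a rare complication should not be read as evidence of safety.

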During the operation, a pulse oximeter will be used to monitor and record the patient's oxygen saturation. The patient's gender, height, weight, BMI, age, past medical history, ASA classification, type of laryngoscopic surgery, operation time, lesion location, blood loss, and anesthesia records will be kept.

All three groups of patients will use radial artery catheters. In addition, the three groups performed arterial blood gas analysis (including: PaO₂, PaCO₂, pH, HCO₃⁻) at the following times to understand the difference of pCO₂ in different groups and as a secondary result.

The first period to measure those variables is before each set of surgery are follows:

The first group is before tracheal intubation.

The second group was before the administration of muscle relaxants.

The third group is before applying superior laryngeal nerve block bilaterally.

The second period to measure those variables is the end of the operation.

The third period to measure those variables is 15 minutes after entering the recovery room.

All the anesthesia time, operation start time and operation end time of the three groups will be recorded, and the relationship between them will be discussed.

After the operation, the surgeon and the patient will be asked to do a questionnaire survey in order to understand whether the non-intubation anesthesia laryngoscope microsurgery of the self-breathing causes obstruction or other difficulties for the operator, as well as the patient's postoperative recovery, surgical satisfaction and operation After scoring. Finally, the surgeon's score on the degree of surgical completion was taken as the primary outcome.

Conditions for participating in this research project:

- Subjects are between 20-80 years old.
- Patients undergoing laryngoscope microsurgery.

- Anesthesiologists rated ASA as between I and III.

If those who are included have any of the following conditions, you will not be able to participate in this research project:

- Having drug dependence and drinking habits.
- Abnormal heart, liver and kidney function.
- Allergic reactions to narcotic drugs.
- Emergency surgery.
- pregnancy.
- Refuse to participate.

This study will explore the following assumptions:

Ho1: The intraoperative field of vision of the nonintubation group is clearer than that of the intubation group.

Ho2: Non-intubation and no muscle relaxation has less carbon dioxide retention and less hypercapnia.

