Table VII. The surgeon was satisfied with the surgical satisfaction of the three groups, but the stress intensity was higher when performing non-intubation and nerve block surgery.

Table VIII. Dunnett T3 Post-hoc tests of during the operation

variable			M.D (I-J)	SE	p-value
pH_2	G1	G2	.135961*	.024404	.001
		G3	-.013455	.017469	.825
	G2	G1	-.135961*	.024404	.001
		G3	-.149416*	.024411	.000
	G3	G1	.013455	.017469	.825
		G2	.149416*	.024411	.000
PaCO2_2	G1	G2	-32.0468*	8.5162	.020
		G3	-1.1636	3.9766	.987
	G2	G1	32.0468*	8.5162	.020
		G3	30.8831*	8.8281	.023
	G3	G1	1.1636	3.9766	.987
		G2	-30.8831*	8.8281	.023
PaO2_2	G1	G2	-134.9130	52.1401	.087
		G3	-155.0273*	45.5545	.012
	G2	G1	134.9130	52.1401	.087
		G3	-20.1143	63.6399	.984
	G3	G1	155.0273*	45.5545	.012
		G2	20.1143	63.6399	.984

*. The M.D is significant at the 0.05 level.

[figure not shown]
Table VIII. Found the following situation :

1. In the non-intubated and muscle relaxant group (G2), the pH value during the operation was lower than the non-intubated and nerve-blocking group (G3), and lower than the normal value (7.35-7.45) .
2. During the operation, the PaCO2 of the non-intubated and muscle relaxant group (G2) was significantly higher than intubated group and also higher than the non-intubated and nerve-blocking group.
3. The PaO2 value of the intubation group (G1) during the operation was lower than that of the non-intubation group.

KSVGH20-C9-09 CASE REPORT

No:	Consent Signed _(MM/DD/YYYY) :	Operation Date:				
Patient status : _____						
Reason for quitting :						
Gender:	Age:	Weight _(kg) :	Height _(cm) :	BMI:	ASA:	
BASELINE MEDICAL/SURGICAL HISTORY :						
Time to enter the room :		Before induction BT:_____ SpO ₂ :_____ BP:___/___ PR:___ RR:___				
Study Group		Operation time				
Induction time		Anesthesia time				
Endo size & pressure		Propofol dose		Rocuronium dose		
		Fentanyl dose		Cisatracurium dose		
GAS		Before(:) G1: intubation ; G2: cis and scc ; G3: SLNB		OP end(:)		
pH				POR(:)		
PaCO ₂						
PaO ₂						
SO ₂ %						
HCO ₃ ⁻						
Time to post anesthesia recovery room :						
BT:_____ SpO ₂ :_____ BP:___/___ PR: ___ RR:_____						
PACU	Time	oxygen	respiration	circulation	consciousness	activity

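### Two second-year primary outcomes are each tested at 0.05 with no rule joining them, so the chance of a false primary claim is up to about 10%, not 5%

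*Protocol*

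**What the plan says.** All of this is in section C of the protocol.

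- **Significance level.** Item 5 of the statistical analysis list: "all statistical tests will be two-way and evaluated at a significance level of 0.05". The item allows for exceptions, but the protocol states none.
- **Primary outcomes, second year.** Two are listed: "Less carbon dioxide retention and less hypercapnia" and "Reduce postoperative lung complications". No sentence says whether either one suffices or both are needed.
- **Another primary outcome.** The paragraph on the postoperative questionnaires says that "the surgeon's score on the degree of surgical completion was taken as the primary outcome". The paragraph on arterial blood gases describes the pCO2 comparison "in different groups and as a secondary result".
- **Hypotheses.** Ho1 to Ho5 are introduced with "This study will explore the following assumptions". Only Ho2 (carbon dioxide) and Ho4 (lung complications) correspond to the second-year primary outcomes.
- **Three-group test.** Item 3: "The difference between the three groups was analyzed using one-way ANOVA". Item 4 adds chi-square or Fisher's exact test for group differences and does not say whether these are overall or pairwise.
- **Pairwise tests shown.** Table VIII reports Dunnett T3 comparisons for three intraoperative blood-gas variables in the first 29 patients, with the footnote "The M.D is significant at the 0.05 level".
- **Sample size.** 30 per group, from 80% power, one 5% alpha, a 25% reduction in incidence and 10% loss.

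**The concern.** A 5% error rate belongs to one test, or to a set of tests joined by a rule. Here the protocol declares more than one primary outcome and gives each the full 0.05. If a significant result on either second-year primary outcome would be reported as a positive trial, the trial has two chances of a false positive, and the 5% in the sample size paragraph no longer describes its error rate. If both had to succeed, the rate would be at most 5% and no split would be needed. The protocol does not choose.

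A further difficulty is that section C is not consistent about which outcome is primary: completion score in one place, carbon dioxide and lung complications in another, with pCO2 also called secondary. Until that is settled, nobody can say which test carries the 5%.

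**Working it through.** **1. The plan's own figure.** The protocol gives no base rate, so 25% versus 0% (equivalently 100% versus 75%) is an assumption. With z(0.975) = 1.960, z(0.80) = 0.842 and mean proportion 0.125:

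n = [1.960 × √(2 × 0.125 × 0.875) + 0.842 × √(0.25 × 0.75)]² / 0.25² = 26.3, so 27 evaluable, and 27 / 0.90 = 30 per group.

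This matches the stated 30. It spends the whole two-sided 5% on one comparison of one outcome.

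**2. Chance of at least one false primary claim, all nulls true.** For k independent tests at 0.05 it is 1 − 0.95^k.

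- k = 2 (the two second-year primary outcomes): 1 − 0.95² = 9.75%.
- k = 3 (completion score also primary): 1 − 0.95³ = 14.3%.

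**3. Correlation between the outcomes.** Simulating an overall one-way ANOVA on each of two normal outcomes, three groups of 30, gives 9.7% at correlation 0, 8.0% at 0.8 and 6.5% at 0.95.

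**4. A discrete complication outcome.** The protocol gives no lung-complication rate, so a range is assumed. The true size of the overall three-group test at 30 per group, by exact enumeration, is combined with one independent 5% carbon dioxide test as 1 − 0.95 × (1 − size):

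| Assumed rate | Overall chi-square: size | With CO2 | Overall Fisher: size | With CO2 |
|---|---|---|---|---|
| 2% | 2.0% | 6.9% | 0.3% | 5.3% |
| 5% | 3.6% | 8.4% | 1.8% | 6.8% |
| 10% | 4.0% | 8.8% | 3.6% | 8.4% |
| 30% | 5.2% | 9.9% | 4.3% | 9.1% |

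So the rate is about 5% to 9% for rare complications and about 10% at most.

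**5. Were the pairs shown already adjusted?** For PaCO2 during surgery, G1 versus G2 in Table VIII, t = 32.0468 / 8.5162 = 3.76 on 6.95 Welch degrees of freedom. The unadjusted p is 0.0071; Dunnett T3 gives 0.0199, against the stated .020. For G2 versus G3 the unadjusted p is 0.0082 and T3 gives 0.0229, against the stated .023. The three pairs within a blood-gas variable were therefore adjusted. With T3-like adjusted pairs on both outcomes the simulated rate is 8.6%; with pairs tested only after a significant ANOVA it is 9.7%.

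**6. Effect of splitting alpha.** Two tests at 0.025 give 1 − 0.975² = 4.94%. On the 25% versus 0% assumption with 27 evaluable per group, power is Φ[(√27 × 0.25 − z × 0.4677) / 0.4330]: 81% at 0.05 (z = 1.960) and 72% at 0.025 (z = 2.241).

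For carbon dioxide, the PaCO2 means and SDs during surgery in Table II give, at 30 per group, (86.4 − 55.5) / √[(21.7² + 10.8²) / 30] = 30.9 / 4.43 = 7.0 standard errors for G2 versus G3. The stricter threshold costs this outcome practically nothing.

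**The case against.** The best defence is that multiplicity rules are often left to the statistical analysis plan, which is not shown, and that item 5 allows for exceptions. That would answer a protocol that was silent. This one declares several primary outcomes and fixes 0.05 for every test; a later document could change that rule, but as written it stands.

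A second defence is that 9.75% is an upper figure. That is right. It assumes that both nulls are true, that the outcomes are independent and that success on either one counts. Correlation or rare complications lower it.

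Some larger readings are tempting, and the protocol does not support them.

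- **About 23%.** A reader might count five hypotheses at 0.05 (1 − 0.95⁵ = 22.6%) or three unadjusted pairs on each of two outcomes (22.8% simulated). But Ho1 to Ho5 are only to be explored, and Ho1, Ho3 and Ho5 are not second-year primary outcomes. Item 3 plans an overall three-group test, and the only pairwise tests shown are adjusted. It is true that Dunnett T3 appears only in the results table and that item 4 leaves open whether complications are tested in pairs. That is a reason to name the test, not evidence of unadjusted pairs.
- **About 9% from two looks.** A reader might treat the tables on the first 29 patients as an interim look at which success could be claimed. The protocol reports them as progress and continues to 90, with no early-claim or stopping rule. No row in those tables is labelled lung complications.

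**Conclusion.** The point holds for the two second-year primary outcomes. Followed as written, and with success on either outcome counted as success, the chance of at least one false primary claim is up to about 10%: 9.75% under independence, and about 5% to 9% if complications are rare and tested overall by chi-square or Fisher at assumed rates of 2% to 10%. If the completion score is also primary, the bound is about 14%. In practice it would add little, because completion was 100% in every group so far and Table VI could give no test. If both outcomes had to succeed, there would be no inflation, but the protocol does not say so.

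This should be corrected, but it does not invalidate the trial.

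**What to change.** 1. **Reconcile the primary outcome.** Make the questionnaire paragraph, the blood-gas paragraph and the second-year list agree on whether completion score, carbon dioxide and lung complications are primary. This comes first, because no error rate can be set without it, and no outcome should be demoted silently.
2. **In item 5, state one primary test for each primary outcome:** either the overall three-group test already planned or one named contrast.
3. **Apply Holm across those tests.** For two outcomes: the smaller p-value at 0.025, then the other at 0.05. For three: 0.0167, then 0.025, then 0.05.
4. **Label everything else secondary or exploratory, with 95% confidence intervals:** pairwise comparisons beyond the primary test (Dunnett T3 for blood gases, Holm-adjusted Fisher for categorical outcomes), all other hypotheses, and every p-value from the first 29 patients.

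One test per outcome matters. If success on a first carbon dioxide contrast both passed alpha to lung complications at 0.05 and opened a second carbon dioxide contrast at 0.025, the same alpha would be spent twice. With a real first contrast and the other nulls true, the error would be 1 − 0.95 × 0.975 = 7.4%.

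The cost is one paragraph and a slightly stricter first step. For a binary outcome on the assumed 25% versus 0%, power is about 72% at 0.025 and returns to about 81% once carbon dioxide succeeds. Keeping 80% power at 0.025 without relying on that would need 32 evaluable, or 36 per group (32 / 0.90 = 35.6).

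### The 80% power at 30 per group for a 25% incidence reduction has no reference rate, scale or driving event, so it holds only under unstated choices and is not a general property of the design

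*Protocol*

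**What the plan says.** All references are to Protocol section C, Methods and study procedure, unless stated.

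- **Sample size calculation, events:** "The main purpose of the study will focus on the completion of surgery and the occurrence of complications".
- **Sample size calculation, inputs:** the aim is to "detect a difference in incidence reduction of 25%. A statistical power of 80%, a 5% alpha and up to 10% possible sample loss".
- **Sample size calculation, result:** "Therefore, each group will require 30 patients (90 in total").
- **Statistical analysis, item 3:** "The difference between the three groups was analyzed using one-way ANOVA". The sentence goes on to intubation versus non-intubation, listing complications and degree of completion among the variables.
- **Statistical analysis, item 4:** "The differences between the groups will be evaluated by chi-square test or" Fisher's exact test. Item 5 makes tests two-sided at 0.05.
- **Primary outcome, before the eligibility criteria:** the surgeon's completion score is primary, and the blood gas comparison of pCO2 is a secondary result.
- **Primary outcome (2nd year):** "Less carbon dioxide retention and less hypercapnia" and "Reduce postoperative lung complications". Ho4 matches the second of these: "Non-intubation and no muscle relaxation may lead to less postoperative pulmonary complications".
- **Table VI:** completion is 11/11, 7/7 and 11/11, with the test marked as not suitable for statistics.
- **Results in the opening summary:** the 29 patients count towards the 90, with 61 still to come.

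**The concern.** A two-proportion sample size needs two rates, a contrast and a test. The paragraph supplies a difference, the power, the alpha and the loss, then draws N as if these sufficed. A finished calculation appears in this document, so its missing inputs are not something the protocol merely leaves to an SAP.

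The 80% is attached to two different events. One is completion, where no failure has been seen. The other is complications, for which no rate is given in the calculation. A reader who relies on the 80% cannot tell which comparison has it. A null result could then be read as coming from an adequately powered comparison when it did not.

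**Working it through.** **Inputs from the Protocol:** difference 25%, power 80%, two-sided alpha 0.05, loss 10%, 30 per group. **Assumed here:** every reference rate, because none is stated.

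**1. Reproducing 30.** Pairwise pooled-variance formula, with p̄ the mean of the two rates:

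n = [1.960·√(2p̄(1−p̄)) + 0.842·√(p1(1−p1) + p2(1−p2))]² / (p1−p2)², rounded up, then divided by 0.9 and rounded up.

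For 25% vs 0%, p̄ = 0.125. The two terms are 0.917 and 0.364, so n = (1.281)²/0.0625 = 26.3, giving 27, and 27/0.9 = 30. By symmetry 100% vs 75% gives the same. The plan's figure is therefore attainable.

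**2. The same inputs at other rates.**

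| Assumed rates | n before loss | n after 10% loss |
|---|---|---|
| 25 vs 0%, or 100 vs 75% | 27 | 30 |
| 30 vs 5% | 36 | 40 |
| 35 vs 10% | 43 | 48 |
| 50 vs 25% | 58 | 65 |
| 62.5 vs 37.5% | 62 | 69 |
| Relative 25%: 30 vs 22.5% | 540 | 600 |

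**3. Power by contrast and test** (exact enumeration; chi-square uncorrected).

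| Contrast | Rates | Fisher | Chi-square |
|---|---|---|---|
| Pairwise, 27 vs 27 | 25 vs 0% | 70% | 93% |
| Pairwise, 30 vs 30 | 25 vs 0% | 80% | 96% |
| Pairwise, 27 vs 27 | 30 vs 5% | 55% | 75% |
| Intubated vs pooled non-intubated, 27 vs 54 | 30 vs 5% | 82% | 87% |
| Intubated vs pooled non-intubated, 27 vs 54 | 50 vs 25% | 56% | 61% |

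A three-group 2-df chi-square with 27 per group (noncentral approximation) has 80% power at 30/5/5% and 51% at 50/25/25%.

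**4. Completion.** Failure here means partially complete or incomplete. With 0 failures in m patients, the exact two-sided 95% upper limit is 1 − 0.025^(1/m).

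- One group: 28.5% for 0/11 and 41.0% for 0/7. Both include 25%.
- Both non-intubated groups together: 18.5% for 0/18. At a true 25% failure rate in both, the chance of 0/18 is 0.75^18 = 0.006.
- If 25% means fewer failures, 0/29 leaves no observed failure to reduce.

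**5. Complications.** An absolute reduction of 25 points requires a reference rate of at least 25%. No rate is given for lung complications. The nearest tabulated symptom is difficulty breathing in Table III: 0/11, 0/7 and 1/11. Sore throat is 3/11, 0/7 and 4/11 in Table III, but the opening summary reports one case each in groups 1 and 3. From 3/11 = 27.3% a 25-point fall is possible. From 1/11 = 9.1% it is not. The p-value printed in Table III (0.20) matches 3/0/4 (chi-square p = 0.203); 1/0/1 would give 0.71.

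**The case against.** The strongest reply is that the figure is correct: 100% vs 75% gives exactly 27/0.9 = 30, and for completion the absolute and relative scales coincide there. This stands, so the point is an unstated assumption and not an arithmetic error.

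Three stronger readings are tempting, and the document does not support them.

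- **No comparison is named anywhere.** Items 3 and 4 describe three-group and intubated versus non-intubated comparisons. What is missing is which of them drives N. Under the pooled contrast, power exceeds 80% at 30% vs 5%, so the trial cannot simply be called underpowered.
- **The interim data rule out a 25-point difference in completion.** They do not for a single group, since 25% lies inside both single-group limits.
- **Completion can no longer reach significance.** In a three-group uncorrected chi-square, 3 failures in one group and none elsewhere give p = 0.044–0.045. With a 25% failure rate among that group's remaining patients (19 in group 1 or 3, 23 in group 2), the chance of at least 3 failures is 89% or 95%, and 80% or 91% if three of those patients are lost. In any case, interim data do not refute a design-stage power statement.

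The choice between Fisher and chi-square may also be left to an SAP. It is shown here only because the 80% depends on it.

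**Conclusion.** The concern holds in limited form. The stated inputs do not determine 30 per group. On the absolute scale the pairwise requirement runs from 30 to 69, and on the relative scale it is 600 at a 30% reference. The 80% is right for some combinations of rates, contrast and test and wrong for others. Even at the boundary rates that reproduce N, pairwise Fisher power with 27 evaluable per group is 70%.

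For completion, the claim rests on a fall from 100% to 75% that the Protocol does not state. The 29/29 record gives no sign of such a fall, and a 25% failure rate in both non-intubated groups fits that record poorly. The two lists of primary outcomes leave open which outcome the power statement should serve.

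The power figures rest on the assumed rates shown and on independent binomial outcomes. The finding that N is undetermined rests on neither. This should be fixed, but it does not call for a larger trial.

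**What to change.** Keep 30 per group and rewrite the sample size paragraph.

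1. Settle one primary outcome between completion (with PaCO2 secondary) and the second-year list of CO2 retention and lung complications.
2. For that outcome, state the event, the contrast (three-group, pairwise, or intubated vs pooled non-intubated), the absolute reference rates and the test. Label rates as assumptions where no data exist. Replace the general 80% with the power that 27–30 per group delivers. For example, if lung complications are chosen with a pairwise test, 10% vs 0% gives 5–7% (Fisher) or 28–35% (chi-square), and 30% vs 5% gives 55–63% or 75–78%.
3. For completion, either say that the 80% rests on 100% vs 75% and that the data so far give no sign of this, or drop the power claim and report exact 95% intervals by group. With no failures in 27 to 30 patients, the upper limit is 12.8% to 11.6%.
4. If sore throat supplies a reference rate, first reconcile the opening summary (one case each in groups 1 and 3) with Table III (3 and 4).

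The cost is text and one count to check, with no extra patients. The sponsor gives up or narrows the favourable 80% statement.
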